2.3.2 Potential Benefits

The study patient participants will not have any direct benefit to their health beyond that of their planned periodontal therapy. The research may help advance periodontal care and may contribute to clinical guidelines for NSPT. No direct benefit to study practitioners is expected.

3 OBJECTIVES AND OUTCOME MEASURES

3.1 Primary

Objective	Brief Description/Justification of Outcome Measure	Outcome Measured By	Time Frame
Assess the effectiveness of SRP plus AMXM compared to SRP with placebo in periodontitis individuals at baseline, reevaluation (6 weeks), and final visit (12 months) following intervention.	The primary outcome of treatment effectiveness will be assessed by full-mouth probing depth (PD) at 6 weeks to 12 months post-intervention adjusted for baseline PD. These are considered universal, standard assessments used to determine periodontal status (Tonetti et al. 2018). A double-blinded patient participant-randomized design is used to assign patient participants to SRP plus AMXM versus SRP plus placebo prior to treatment.	Outcome: Probing Depth (PD) in millimeters. Full- mouth PD measurements (excluding 3rd molars) will be obtained utilizing a UNC 15mm periodontal probe. Level of analysis: site Outcome Type: continuous	Baseline, Re- evaluation (6 weeks), and Final study visit (12 months) after intervention.

3.2 Secondary

Objective	Brief Description/ Justification of Outcome Measure	Outcome Measured By	Time Frame
Assess changes in periodontal tissue attachment comparing SRP plus AMXM to SRP plus placebo in periodontitis individuals at baseline, reevaluation (6 weeks), and final visit (12 months) following intervention.	This secondary objective will be assessed by clinical attachment level (CAL) changes from baseline to 6 weeks to 12 months post-intervention, adjusting for baseline CAL. CAL is a disease-related characteristic. The assessment will employ a validated diagonal protocol (Vettore MV et al. 2007) including one maxillary and one mandibular quadrant to evaluate CAL.	Outcome: Half-mouth CAL in millimeters (excluding 3rd molars) will be obtained utilizing a UNC 15mm periodontal probe to measure base of pocket to cementoenamel junction (CEJ). Level of analysis: site Outcome Type: continuous	Baseline, Re- evaluation (6 weeks), and Final study visit (12 months) after intervention.

Objective	Brief Description/ Justification of Outcome Measure	Outcome Measured By	Time Frame
Assess changes in the probability of bleeding on probing (BoP) at a given site comparing SRP plus AMXM to SRP with placebo in periodontitis individuals at baseline, reevaluation (6 weeks), and final visit (12 months) following intervention.	This secondary objective will assess changes in the probability of observing BoP, a common surrogate for gingival inflammation, at 6 weeks to 12 months post intervention, adjusting for baseline BoP. The assessment will utilize a diagonal protocol (one maxillary and one mandibular quadrant) to evaluate BoP.	Outcome: BoP is assessed in conjunction with probing depths using a UNC 15mm periodontal probe and is recorded as a binary outcome per site, i.e., is the site bleeding? Yes/No Level of analysis: site Outcome Type: binary (no/yes)	Baseline, Re- evaluation (6 weeks), and Final study visit (12 months) after intervention.
Assess the reduction in diseased sites comparing SRP plus AMXM to SRP with placebo in periodontitis individuals at baseline, reevaluation (6 weeks), and final visit (12 months) following intervention.	Reduction in diseased sites is a calculated variable from PD. We will assess the probability a site is observed with residual PD≥ 5 mm at 6 weeks to 12 months post-intervention, adjusting for its baseline PD. This is a common outcome related to the primary outcome (change in PD), which better reflects further treatment needs.	Outcome: PD≥ 5mm; The maximum probing depth per tooth will be recorded as ≥5 mm (yes/no). Level of analysis: site Outcome Type: binary (no/yes)	Baseline, Re- evaluation (6 weeks), and Final study visit (12 months) after intervention.
Assess disease remission between arms of SRP plus AMXM compared to SRP with placebo in periodontitis individuals at baseline, reevaluation (6 weeks), and final visit (12 months) following intervention.	Disease remission is defined as the number of study patient participants who have ≤4 sites with PD≥5mm (Feres et al. 2020). This variable is calculated from PD≥ 5mm.	Outcome: Number of patient participants with ≤4 sites with PD≥ 5mm; Patient participants will be considered 'in remission' if they display ≤4 sites with PD≥ 5mm; This is a dichotomization from the summation of PD≥ 5mm within person.	Re-evaluation (6 weeks), and Final study visit (12 months) after intervention.
		Level of analysis: person Outcome Type: binary (no/yes)	

Objective	Brief Description/ Justification of Outcome Measure	Outcome Measured By	Time Frame
Evaluate patient- reported changes in oral health-related quality of life comparing SRP plus AMXM to SRP with placebo in periodontitis individuals at baseline, re- evaluation (6 weeks), and final visit (12 months) following intervention.	To evaluate oral health-related quality of life, the Oral Health Impact Profile (OHIP-5) will be utilized. The OHIP-5 is an abbreviated patient-reported outcome measure (PROM) that gauges oral-health related quality of life status (John 2022). This provides insight on the patient participant's perception of their individual oral health status.	Outcome: OHIP-5 sum score based upon self-reported responses. Level of analysis: person Outcome Type: continuous	Baseline, Re- evaluation (6 weeks), and Final study visit (12 months) after intervention.
Evaluate treatment - related adverse events. (Safety outcome)	The number and severity of adverse events related to SRP plus AMXM versus SRP plus placebo will be recorded to assess the safety of the intervention.	Outcome: Number of serious adverse events (SAEs) and adverse events (SAEs) and adverse events (AEs) identified by practitioners at each study visit, or at unscheduled encounters related, probably related, or possibly related to study participation, during the study period. Documentation of SAEs and AEs will identify if the event was unexpected/expected and unrelated/related to study participation or the intervention, following relevant OHSP reporting procedures for SAEs and AEs.	Continuously throughout the study.

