6.7 Study Procedural Intervention(s) Description and Administration

The procedural intervention in this trial is SRP. As described above, SRP entails the mechanical debridement of the root surfaces of teeth as part of periodontal treatment (Badersten et al. 1981). The same procedural intervention will be applied to both arms by operators who will be blinded to the arm allocation of each patient participant. Based on state licensure and routine clinical practice of each dental practice site the SRP may be performed by either the dentist practitioner or by their hygienist. The "PAAS Baseline Visit Checklist" will capture data on whether a dentist or hygienist is completing the visit.

In the training slides it is suggested that all SRP procedures are performed with local dental anesthesia or Topical anesthetic (e.g., Oraqix); this information will be also captured in the "PAAS Baseline Visit Checklist". Adequate completion of SRP will be determined with an appropriate calculus explorer as per standard clinical procedures, and relevant training is provided in the training videos. The intervention will be applied once at each involved quadrant either at the baseline visit or the optional second baseline visit with at least one quadrant completed at the first visit. The drug / placebo loading dose will be performed prior to SRP for the 1st baseline visit, regardless of the number of baseline visits. The second baseline visit should occur within 10 days of the initial baseline visit. If the second baseline visit has not happened within 30 days from initiation of the investigational product (drug / placebo), the patient participant is discontinued from study, and this will be considered as missing data.

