9.1.2 Adverse Events

An adverse event is any untoward or unfavorable medical occurrence in a human subject, including any abnormal sign (for example, abnormal physical exam or laboratory finding), symptom, or disease, temporally associated with participation in the research, whether or not considered related to the patient participant's participation in the research.

Practitioners will record information about the adverse event from the patient participant. The study PI should review the report and confirm the practitioner's assessment on whether it identifies the adverse event as being:

- 1. unexpected
- 2. related or possibly related to participation in the research
- serious or otherwise one that suggests that the research places patient
 participants or others at a greater risk of physical or psychological harm than was
 previously known or recognized

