9.3.1 Relationship to Study Intervention

To assess relationship of an event to study intervention the following guidelines are used:

- 1. Related (Possible, Probable, Definite)
 - a. The event is known to occur with the study intervention, and/or
 - b. There is a temporal relationship between the intervention and event onset and/or
 - c. The event abates when the intervention is discontinued, and/or
 - d. The event reappears upon a re-challenge with the intervention.
- 2. Not Related (Unlikely, Not Related)
 - a. There is no temporal relationship between the intervention and event onset, and/or
 - b. An alternate etiology has been established

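### The safety outcome is limited to events judged related, but the relatedness rule in 9.3.1 can class one event both ways and the attribution target changes between sections

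*Protocol*

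**What the plan says.** The safety row of section 3.2 has the objective "Evaluate treatment - related adverse events". Its outcome is the number of serious and non-serious events identified at study visits or unscheduled encounters, qualified as "related, probably related, or possibly related to study participation, during the study period". The same row asks that each event be documented as "unrelated/related to study participation or the intervention". The Protocol Summary also lists treatment-related events as the between-group safety comparison.

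Collection is wider. Section 9.1.2 defines an adverse event "whether or not considered related to the patient participant's participation in the research", and section 9.2 records all events from consent until after the last day of participation.

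Section 9.3.1 gives the only rule for relatedness. Related has four criteria, including "The event is known to occur with the study intervention, and/or" and "There is a temporal relationship between the intervention and event onset and/or"; the others are that the event abates on discontinuation or returns on re-challenge. Not Related has two: no temporal relationship, and/or "An alternate etiology has been established". No order of precedence is stated.

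Section 6.7 says "The procedural intervention in this trial is SRP" and applies it to both arms. Section 9.3.2 lists six expected events. Three follow the procedure (tooth sensitivity, pain, abscess) and three are drug-type (nausea and two forms of allergic reaction).

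**The concern.** The protocol collects everything and then narrows its safety outcome through a judgment. If the rule behind that judgment can give two answers for the same facts, the count depends on who applies it and how. If the target of the judgment is not fixed, an event caused by SRP may or may not enter the count.

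The trial is meant to inform when adjunctive antibiotics are justified, so what AMXM adds in harm over placebo is a central result. Randomization and masking can supply that contrast without individual causality calls. Filtering on such calls adds misclassification. Totalling procedure events common to both arms with drug events would also make a relative comparison harder to read.

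**Working it through.** The protocol gives no rate, power or sample size for the safety outcome, so there is no stated figure to reproduce.

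**1. The 9.3.1 rule.** It uses five yes/no facts: known to occur (K), temporal relationship (T), abates (A), reappears (R), alternate etiology (E). With and/or taken as any one sufficing:

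- Related = K or T or A or R
- Not Related = (not T) or E

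There are 2^5 = 32 combinations.

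- T present (16): all are Related. The 8 with E are also Not Related. So 8 meet both and 8 are Related only.
- T absent (16): all are Not Related. The 14 with at least one of K, A, R are also Related. So 14 meet both and 2 are Not Related only.

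In total 8 + 14 = 22 meet both, 8 Related only, 2 Not Related only, 0 neither.

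Twelve of the 22 (T absent, with A or R present) are scarcely coherent clinically. Leaving them out, 10 of the remaining 20 still meet both. Nausea during dosing with another established cause is an ordinary example.

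**2. The attribution target.**

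| Section | Target of attribution, or place of SRP |
|---|---|
| 3.2 | "unrelated/related to study participation or the intervention" |
| 9.3.1 | the study intervention |
| 9.1 | the intervention and the procedures |
| 4 | drug or placebo together with SRP as one intervention |
| 6.7 | SRP is the procedural intervention |
| Appendix A | medication and SRP on separate rows |

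The labels differ too. Section 3.2 has related, probably related and possibly related; 9.3.1 has Possible, Probable and Definite.

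**3. What totalling could do (illustration only).** From the protocol: n = 272 per arm (12.2) and two-sided alpha 0.05 (12.4). Assumed, with no source in the documents: drug-type events at d = 5% on placebo and 15% on AMXM, and an SRP-type background s that is equal in both arms and independent of drug events.

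- Participants with any event: p = 1 − (1 − s)(1 − d). Power = Φ{[Δ − 1.96√(2p̄(1 − p̄)/n)] / √[(p0(1 − p0) + p1(1 − p1))/n]}.
- Event counts per person: λ = s + d. Power = Φ{0.10/√[(λ0 + λ1)/n] − 1.96}.

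Example at s = 30%, any event: p0 = 1 − 0.70 × 0.95 = 0.335, p1 = 1 − 0.70 × 0.85 = 0.405, p̄ = 0.37. Power = Φ[(0.07 − 0.0811)/0.0413] = 0.394.

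| s | Any event, placebo vs AMXM | Ratio | Power | Count ratio | Power (counts) |
|---|---|---|---|---|---|
| 0 (drug-type alone) | 5.0% vs 15.0% | 3.00 | 97.5% | 3.00 | 95.8% |
| 10% | 14.5% vs 23.5% | 1.62 | 76.4% | 1.67 | 74.1% |
| 20% | 24.0% vs 32.0% | 1.33 | 54.7% | 1.40 | 56.7% |
| 30% | 33.5% vs 40.5% | 1.21 | 39.4% | 1.29 | 45.4% |
| 40% | 43.0% vs 49.0% | 1.14 | 28.9% | 1.22 | 37.8% |
| 50% | 52.5% vs 57.5% | 1.10 | 21.5% | 1.18 | 32.5% |

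The difference in counts is λ1 − λ0 = 0.10 per person in every row. The shared background lowers the ratio and the precision and leaves that difference unbiased.

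**The case against.** **The restriction may be narrower than it looks.** The related phrase in 3.2 directly follows the unscheduled encounters and could qualify only those. The stated objective and the Protocol Summary both speak of treatment-related events, so the wider restriction is the better reading, though the phrase alone does not settle it.

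**Drug and SRP are partly separated already.** Appendix A lists them apart. The discontinuation and re-challenge criteria in 9.3.1 fit a drug course, as does the use of intervention in 5.5 and 9.4.3. Section 9.1 can be read as asking for two attributions. This stands: the fault is inconsistent usage without a rule for two attributions, and it does not prove that drug attribution is absent.

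**No pooled endpoint is defined.** Section 3.2 gives number and severity and names no any-related-event composite, and 12.4 names no AE model. Tabulation by event type may be in the SAP, which is not at hand. This also stands, so the power table describes a possible use of the data and does not describe a planned test.

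**The judgment is reviewed.** The PI grades relationship (9.1) and confirms the practitioner's assessment (9.1.2), and 9.3.1 calls its criteria guidelines. Review makes calls more uniform, but it does not say which class wins when both are met.

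A reader might infer that SRP events hide the antibiotic's harms, or that an empty safety contrast would wrongly support antibiotic use. The documents do not support either. Attribution is blinded, SRP is common to both arms, severity and serious events are recorded, and unrelated events stay in the database. Nor does the absence of planned safety analyses in 12.3.1 rule out a final comparison, since that statement sits under interim analyses.

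**Conclusion.** The point holds as a defect in how the safety outcome is defined. The outcome passes through a relatedness filter that is not well defined: 22 of 32 logical patterns meet both classes, which says nothing about how often real events would. The attribution target and the labels also differ between sections. The contrast that randomization and masking already provide does not need this judgment.

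The dilution argument is conditional. It applies only if SRP-type and drug-type events are totalled, and its size rests wholly on assumed rates. In the illustration, power for a 5% versus 15% drug-event difference falls from 97.5% to 76.4% at a 10% background and to 21.5% at 50%. The difference in counts is not biased.

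An all-event comparison remains recoverable from the data. Unless it is prespecified, however, it would depart from the outcome stated in 3.2. The protocol should be corrected, but the point does not threaten the trial's validity.

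**What to change.** In 3.2, and to match in the Protocol Summary, define the safety outcome as all AEs and SAEs starting after the first dose, compared by arm regardless of relatedness. Report two groups separately: drug-type events (nausea, diarrhea, fungal or yeast infection, allergic reaction) and SRP-type events (sensitivity, pain, abscess). Keep related events as a supporting table. The split is essential, because counting all events alone would add shared background.

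In 9.3.1, make the categories mutually exclusive by stating which criterion prevails when both sets are met. Use one set of labels in 3.2 and 9.3.1, and state attribution to study drug and to SRP separately. Align the wording in 9.1.

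The cost is protocol wording, a longer AE table and possibly one more eCRF field (the form is not at hand). All events are already recorded, so no new event collection is needed.

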4 STUDY DESIGN

This is a patient participant-randomized, double-blinded clinical trial that will be conducted in three National Dental PBRN Nodes: Western, South Central and Southwestern Nodes. About 53% of fully participating (level 3) dentists in the National Dental PBRN are located in these three regions and reflect the wide demographic and practice setting diversity of the national membership. Currently, there are 451 active Level 3 dentists in the South-Central region, 540 in the Western region, and 716 in the Southwest region.

This research study will be conducted in the National Dental PBRN and will involve approximately thirty-four practitioners who will enroll a target of N=544 patient participants (a target of n=16 patient participants per practice). Patient participants will be randomly assigned to either AMXM or placebo, in conjunction with SRP as a single intervention. Randomization will be performed in blocks and stratified by practice to mitigate any inter-practice effects. AMXM is the most employed periodontal adjunctive antibiotic therapy based on existing studies (Smiley et al. 2015) and will be compared to non-active placebo.

Brief description of the study design:

- Intervention model: parallel arm, placebo-controlled, randomized clinical trial.
 Test arm (~N=272): AMXM group; control arm (~N=272): placebo group.
- Masking: practitioner- and patient participant-level masking. Statistician assessor will also remain blinded; a separate biostatistician will remain unblinded in order to implement randomization.
- Allocation: patient participant-randomized with randomization stratified by practitioner to mitigate inter-practitioner effects.
- Timepoints: Baseline visit* (intervention), re-evaluation visit (6 weeks post-intervention), and final study visit (12 months post-intervention).

*In case time does not permit completion of SRP at one visit, an optional second baseline visit may occur within 10 days of the first baseline visit.

4.1 Practitioner recruitment

Practitioners will be recruited from three National Dental PBRN Nodes based on specific enrollment criteria including confirmation that they routinely treat patient participants with periodontal disease and have previously administered adjunctive antibiotics with SRP. Most state licensures require that a dentist diagnose periodontal disease, while a dentist or hygienist may perform SRP. Therefore, dentists and hygienists may be recruited and trained for the study depending on the division of care at each practice site (refer to study training slides for more information). Multiple practitioners may be

recruited from the same practice. Case report forms (CRFs) will indicate the type of provider (DDS vs. RDH).

Recruitment and rolling enrollment of practitioners is estimated to take approximately 3-6 months. Once trained, practitioners and office staff will begin to recruit and enroll patient participants. It is expected that each practitioner will enroll a target of 16 patient participants (up-to 22 patient participants) over a 4-6-month period of time. The entire data collection period for each practitioner is expected to be approximately 16-21 months. The study participation duration for patient participants is expected to be approximately 12 months (the expected range is from 10 months to 15 months). Study appointments (baseline, re-evaluation, and final study visit) are expected to add no more than 15 minutes to a typical appointment length of its type.

4.2 Patient participant recruitment

The patient participant population will be enrolled from National Dental PBRN practices without regard to sex, race, or ethnicity. Periodontitis diagnosis will follow the criteria established by the 2018 Classification of Peri-implant Diseases and Conditions. The study will enroll a target of N=544 adult patients aged 40 years, or older with an existing or new diagnosis of Generalized Stage II-III, Grade A-C periodontitis (previously Generalized Moderate to Severe Periodontitis) requiring periodontal treatment. At the time of screening periodontal status will be assessed to determine eligibility based on periodontal examination including probing depth, clinical attachment levels and patient participant characteristics, such as age, smoking and diabetic status according to the classification guidelines (Papapanou et al. 2018).

Intervention: Patient participants will receive conventional SRP (standard of care) with or without adjunctive antibiotics depending on group allocation (AMXM group versus Placebo group respectively). SRP refers to the procedure of mechanically debriding the root surfaces of teeth as part of periodontal treatment (Badersten et al. 1981). The SRP procedure will be provided by the PBRN practitioners or their practices' hygienists. All patient participants will receive SRP; either the entire mouth will be treated at the baseline visit (visit 1) or if determined by the practitioner a second optional baseline visit (visit 1B) may be scheduled within 10 days of visit 1 to complete the SRP. In conjunction with SRP, the patient participants will receive adjunctive AMXM or placebo as the study intervention based on randomized allocation. AMXM is a combination antibiotic comprised of Amoxicillin 500mg and Metronidazole 500mg in two separate capsules. The intervention will be administered in-office starting with a loading dose (1g Amoxicillin and 1g Metronidazole, i.e. two capsules of each medication, or equivalent placebo) of AMXM or placebo followed by a self-administered 10-day course (See Section 6.2). The AMXM or placebo will be provided to participating practitioners in Individual Patient participant Packages (IPPs), labeled and shipped to participating

practices by the Pl's local study team. The IPPs are packages containing all study supplies required for each patient participant including the study drugs, plaque collection supplies and shipping supplies (see MOP).

Data Collection & Analysis: Following randomization, practitioners will obtain periodontal clinical measurements and optional baseline plaque samples, and then proceed with the intervention; i.e., an antibiotic (or placebo) regimen will be initiated, and standard SRP will be performed. Changes in periodontal clinical and patient-reported outcomes (see protocol section 3 for description of outcome) will be assessed at re-evaluation (6 weeks + 3 weeks) and at the final study visit (12 months -2,+3 months; range is 10-15 months) post-intervention. Both disease-oriented clinical outcomes (probing depth changes, attachment level changes, bleeding on probing) and an abbreviated oral health-related quality of life patient-reported outcome (Oral Health Impact Profile-5 (OHIP-5)) will be assessed at all timepoints.

In terms of the dependent variables employed in the analyses, overall there are 5 recorded variables (PD, BoP, CAL, OHIP-5, and AE) and the rest of the variables are calculated from these variables. As discussed in section 3, reduction in diseased sites is a calculated variable from PD by PD≥ 5mm; the maximum probing depth per tooth will be recorded as ≥5 mm (yes/no). Further, the disease remission variable is defined as the number of study patient participants who have ≤4 sites with PD≥5mm (Feres et al. 2020). This variable is calculated from PD≥ 5mm as the patient participants that display ≤4 sites with PD≥ 5mm; this is a dichotomization from the summation of PD≥ 5mm within person. All analyses will be data-level, and changes in site-level dependent variables at each timepoint will be assessed using mixed models to account for the clustering of longitudinal observations (level1) within tooth site (level 2) within patient participants (level 3) and will include a random intercept to account for multi-practitioner effects. Additional information is detailed in section 12.

